# APPENDIX B. AABB FULL-LENGTH DONOR HISTORY QUESTIONNAIRE

The questionnaire provided here is a sample and may have undergone revisions since the protocol was drafted. Only the most recent version in use at the clinical site will be administered to study subjects.

	Yes	No	
Are you			
1. Feeling healthy and well today?			
2. Currently taking an antibiotic?			
3. Currently taking any other medication for an infection?			
Please read the Medication Deferral List.			
4. Are you now taking or have you ever taken any medications on			
the Medication Deferral List?			
5. Have you read the educational materials?			
In the past 48 hours			
6. Have you taken aspirin or anything that has aspirin in it?			
In the past 6 weeks			
7. Female donors: Have you been pregnant or are you pregnant			$\Box$ I
now? (Males: check "I am male.")			am
			male
In the past 8 weeks have you		ı	
8. Donated blood, platelets, or plasma?			
9. Had any vaccinations or other shots?			
10. Had contact with someone who had a smallpox vaccination?			
In the past 16 weeks			
11. Have you donated a double unit of red cells using an apheresis			
machine?			
In the past 12 months have you		_	
12. Had a blood transfusion?			
13. Had a transplant such as organ, tissue, or bone marrow?			
14. Had a graft such as bone or skin?			
15. Come into contact with someone else's blood?			
16. Had an accidental needlestick?			
17. Had sexual contact with anyone who has HIV/AE or has had a			
positive test for the HIV/AE virus?			
18. Had sexual contact with a prostitute or anyone else who takes			
money or drugs or other payment for sex?			

19. Had sexual contact with anyone who has ever used needles to take drugs or steroids, or anything not prescribed by their doctor?			
20. Had sexual contact with anyone who has hemophilia or has used			
clotting factor concentrates?			
In the past 12 months have you (continued)	Yes	No	
21. Female donors: Had sexual contact with a male who has ever had			$\Box$ I
sexual contact with another male? (Males: check "I am male.")			am male
22. Had sexual contact with a person who has hepatitis?			
23. Lived with a person who has hepatitis?			
24. Had a tattoo?			
25. Had ear or body piercing?			
26. Had or been treated for syphilis or gonorrhea?			
27. Been in juvenile detention, lockup, jail, or prison for more than 72 hours?			
In the past three years have you			
28. Been outside the United States or Canada?			
From 1980 through 1996			
29. Did you spend time that adds up to three (3) months or more in			
the United Kingdom? (Review list of countries in the UK.)			
30. Were you a member of the US Military, a civilian military			
employee, or a dependent of a member of the US Military?			
From 1980 to the present , did you			
31. Spend time that adds up to five (5) years or more in Europe?		П	
(Review list of countries in Europe.)			
32. Receive a blood transfusion in the United Kingdom or France?			
(Review list of countries in the UK.)			
From 1977 to the present, have you			
33. Received money, drugs, or other payment for sex?		П	
34. Male donors: Had sexual contact with another male, even once?			
(Females: check "I am female.")			I am
			female
II EVED			
Have you EVER			
35. Had a positive test for the HIV/AE virus?			
36. Used needles to take drugs, steroids, or anything not prescribed by your doctor?			
37. Used clotting factor concentrates?			
38. Had hepatitis?			

39. Had malaria?	
40. Had Chagas' disease?	
41. Had babesiosis?	
42. Received a dura mater (or brain covering) graft?	

Have you EVER (continued)	Yes	No
43. Had any type of cancer, including leukemia?		
44. Had any problems with your heart or lungs?		
45. Had a bleeding condition or a blood disease?		
46. Had sexual contact with anyone who was born in or lived in		
Africa?		
47. Been in Africa?		
48. Have any of your relatives had Creutzfeldt-Jakob disease?		

# APPENDIX D. TELEPHONE RECRUITMENT Recruitment Telephone Call Script

"Hello	My name is	and I am a staff member at Hoxworth Blood Center
I am reaching	g out to you regarding a res	search study that is looking for volunteers. You are being
contacted bed	cause of your history of do	nating blood at our center and because you have
expressed an	interest in participating in	research studies.

# Would you be interested in learning more about our study today?"

- ➤ If No:
  - o "Thank you for your time, we hope you continue to support Hoxworth Blood Center by donating blood in the future."
  - o End the call and record response in the research participant database.
- > If Yes, but not a good time:
  - "Is there a better time to discuss the study with you? Would you like information about the study mailed to your house?"
  - O Arrange for a follow-up call at a later date, AND/OR
  - o Collect information for mailing consent to the potential participant.
- ➤ If Yes:
  - o "Thank you for your interest! Our study is looking at the safety of a new, experimental plasma product called freeze-dried plasma or FDP. Currently hospitals rely on infusions of fresh frozen plasma as definitive care for patients who are bleeding after major surgery or have been in an accident to help control bleeding, fight infection, and restore fluid levels. However, that type of plasma can take a couple of hours to thaw which can be life-threatening for patients who immediately need plasma products. A new method has been developed in which the plasma is 'freeze-dried' instead of frozen. FDP, like fresh frozen plasma, is made from donor plasma, but instead of being frozen it is changed to a powder form for storage through freeze-drying and can be rapidly dissolved back into a liquid form within a few minutes. Because FDP is an experimental product it is not currently approved by the FDA. Participants in the study will donate their own blood or plasma and will receive an infusion of their own reconstituted FDP. The amount of blood or plasma donated and infused depends on which study group you are assigned to. There are a lot of blood tests and some follow-up visits required of people who participate in the study."

# I'd like to go over some pre-screening questions with you to see if you would be a good candidate for participation. Is that OK?

- ➤ If Yes:
  - o "Great, let's get started."
  - o Proceed to next question.
- ➤ If No:
  - o "Thank you for taking the time to speak with me today."

### Do you have any questions about the study so far?

- ➤ If Yes:
  - o Answer all questions until the potential participant is satisfied.
  - o Proceed to next question.
- ➤ If No:
  - o Proceed to next question.

#### Are you currently participating in any other research studies?

- ➤ If Yes:
  - Are you receiving an investigational product in the research study? When do you expect to complete that study?
    - Record answers supplied by the potential participant to discuss with [name]. The exclusion criterion states that participants cannot have received an investigational agent within 1 month of infusion; but does not preclude participation entirely.
  - o "Thank you, I'm not sure if you'll qualify for participation in this study but I'd like to go ahead and complete the rest of the pre-screening questions just in case you are eligible. I'll talk to [name], the investigator for this study, about your responses."
  - o Proceed to next question.
- ➤ If No:
  - o Proceed to next question.

# The expected duration of the study is approximately 4 months. Are you planning on remaining in the area (ex. Not moving out of state, etc.) during that time period?

- ➤ If Yes:
  - Proceed to next question.
- ➤ If No:
  - o "Thank you for your time. Since there are several times throughout the study where you will need to come to Hoxworth Blood Center for tests, we are looking for participants who will be local to Hoxworth Blood Center for the duration of their time in the study."
  - End the call and record response in the research participant database.

#### Would you say your health is generally good?

- ➤ If Yes:
  - o Proceed to next question.
- ➤ If No:
  - o "Thank you for your time; unfortunately for the safety of the study participants we're only enrolling people who believe they are in good health. We hope you continue to support Hoxworth Blood Center donating blood in the future."

#### [For Females Only] Are you pregnant, planning to get pregnant, or currently breastfeeding? > If Yes:

- o "Thank you, unfortunately due to safety reasons we are only enrolling women who are not currently pregnant, planning on getting pregnant, or breastfeeding at this time. We hope you continue to support Hoxworth Blood Center donating blood in the future."
- o End the call and record response in the research participant database.
- ➤ If No:
  - o Proceed to next question.

#### Are you interested in participating in this study?

- ➤ If Yes:
  - o "I would like to set up an initial visit to go over the study in more depth. Attending this initial visit does not commit you to participating in the study. If you consent to participate by signing the informed consent form, you will be screened for all exclusion and inclusion criteria and we will collect blood and urine samples to confirm you are healthy enough to participate. We anticipate this visit could take up to 3 hours."
  - o Schedule the consent and screening visit.
  - o "Thank you for your interest in the study! Your initial visit is scheduled for \_\_\_\_\_\_. Please feel free to contact us if you have any questions about the study in the meantime. If you change your mind about participating in the study, or need to reschedule the screening visit, please contact us.
  - End the call and record response in the research participant database.
- ➤ If No:
  - "Thank you for taking the time to speak with me today. I really appreciate it."

If a printed copy of the Pre-Screening Telephone Call Script is used to document information collected during the call, then it must be maintained as part of the source documentation. If the subject signs a consent and is assigned a subject ID number (SID), then the paper copy of the Pre-Screening Telephone Call Script should be labeled with the SID.

# APPENDIX F. DUKE ACTIVITY STATUS INDEX (DASI)

For each selection in the table, select either yes or no. If the answer is yes, the DSAI value corresponding to the question will be added to the total displayed at the bottom.

Item	Activity	Please C	ircle One	If Yes: DASI Value
1	Can you take care of yourself (eating, dressing, bathing, or using the toilet)?	No	Yes	2.75
2	Can you walk indoors such as around your house?	No	Yes	1.75
3	Can you walk a block or two on level ground?	No	Yes	2.75
4	Can you climb a flight of stairs or walk up a hill?	No	Yes	5.50
5	Can you run a short distance?	No	Yes	8.00
6	Can you do light work around the house like dusting or washing dishes?	No	Yes	2.70
7	Can you do moderate work around the house like vacuuming, sweeping floors, or carrying in groceries?	No	Yes	3.50
8	Can you do heavy work around the house like scrubbing floors or lifting and moving heavy furniture?	No	Yes	8.00
9	Can you do yard work like raking leaves, weeding, or pushing a power mower?	No	Yes	4.50
10	Can you have sexual relations?	No	Yes	5.25
11	Can you participate in moderate recreational activities like golf, bowling, dancing, doubles tennis, or throwing a baseball or football?	No	Yes	6.00
12	Can you participate in strenuous sports like swimming, singles tennis, football, basketball, or skiing?	No	Yes	7.50
		Total	DASI:	

Assessment Done B	y:	Date:	

# APPENDIX H.TELEPHONE FOLLOW-UP SCRIPT Telephone Follow-Up Script

(Administered	48 and 72 hours and 14 day	s after eacl	h Infusion	Visit, for subjects in all Cohorts.)
SID:				
Introductory	Telephone Script:			
Hello,	This is	from H	oxworth B	lood Center following up after
your last study	visit. I would like to ask yo	u some qu	estions abo	out any medical problems
including any center.	medications that you may ha	ve started	taking sind	ce your last visit to the blood
	d the date, time, and visit in ed on the Telephone Follow			ontact. This information will be
	1st 48-Hour Call 2h	d 48-Hour	Call (Coho	ort 3) 1 st
Contact:	72-Hour Call 2 nd 72-l			
Date:				
Time:				
*F	For Cohort 3, the 14-Day Cal	l only take	s place aft	er the second Infusion Visit.
	v the following with the sub ed below.	ject and re	ecord the	responses on the checklist
	e last 24 hours have you he following:	Resp	oonse	Comment
_	ache or migraine?	Yes	☐ No	
Any new vision or hearing defects?		Yes	☐ No	
	of strength or sensitivity in art of your body?	Yes	☐ No	
Chest	pain?	Yes	☐ No	
Short	ness of breath?	Yes	☐ No	
Abdo	minal pain?	Yes	☐ No	

Swollen legs, ankles, or calf pain?	Yes	☐ No				
Rash or unusual bruising on your skin?	Yes	☐ No				
Blood in your urine or stool?	Yes	☐ No				
If the response to any question above		•	1 0 1			
immediately. Reported signs and sym	ipioms are	recorded (	on the Adverse Event CRF.			
2. Are you currently taking any medications since the last visit?	Yes	☐ No				
If yes, write down the name of each medication the subject is taking. Reported medications						
are recorded on the						
Prior and Concomitant Medications CRF.						

- C. Confirm the subject's availability for upcoming study visit:
  - 72-hour telephone contact (if calling for the 48-hour telephone contact); **OR**
  - 7-day on-site visit (if calling for the 72-hour telephone contact).
- D. Complete the Visit Report CRF to indicate the telephone contact took place. The Visit Report CRF is completed after each contact or visit.

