<sup>HMonitor vital signs every 15 minutes during infusion; every 30 minutes for up to 4 hours post-infusion; and after 6 hours, vital signs should be measured every 4 hours until the subject is released. Subjects assessed for DVT, PE, and cardiac ischemia using the Wells Scale prior to infusion, at 30 minutes, 4 hours, and 24 hours post-infusion before the subject can be released from the clinic.

<sup>1Chemistry panel includes Calcium, ALP, ALT, AST, Bicarbonate, Chloride, Glucose, Potassium, Sodium, Total Bilirubin, Total Protein, BUN, Lactate, and Creatinine. pH, Ionized Calcium and Total Magnesium will only be measured at pre-infusion and 0.5 hour post-infusion.

<sup>JSee Table 9 - Laboratory Testing Schedule and Volumes for Cohort 3 for sampling time points.

KCBC comprises Hematocrit, Hemoglobin, Platelet Count, RBC Count, and WBC Count.

<sup>LSPEP is performed on the donated plasma at each plasmapheresis visit.

MCoagulation testing for Factors I, II, V, VII, VIII, IX, X, XI von Willebrand Factor activity, and Total Protein C and S activity.

N Follow-up phone calls to the subject will be made 48 hours and 72 hours following both Infusion Visits. The 14-day follow-up phone call will only occur after Infusion Visit #2.

<sup>o Total Protein can be performed up to 24 hours prior to each subsequent plasmapheresis session.

PAdditional collection visits may be required in the event that a plasma unit experiences an issue during preparation (eg, leakage during transfer to lyophilization bag) or during lyophilization (eg, bag breakage during freeze-drying).

O These tests are for research purposes only and will not be used to manage the safety of study participants.

Table 9: Laboratory Testing Schedule and Volumes for Cohort 3

Laboratory and Coagulation Factor Testing	Screening	Collection Visits		fusion Visit #1 and #2	ts	24-Hour Follow-Up	7-Day Follow-Up	28-Day Follow-Up
			Pre-	Post-I	nfusion	Visits	Visits	Visit
			Infusion	0.5 hr	4 hrs			
Pregnancy Test (females only)	X		X					
Urine Drug Screening	X							
Urinalysis	X		X	X	X	X		
Chemistry Panel A	X		X	X	X	X	X	
CBC B	X		X	X	X	X	X	X
Hematocrit		X						
PT/INR	X		X	X	X	X		X
aPTT	X		X	X	X	X		X
DAT (IgG and C3)	X		X			X		X
Blood Type for ABO and Rh	X		Xc					
Red-Cell Antibody Screen	X							
Syphilis Screen	X							
HTLV Antibody Screening Test	X							

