### 8.3. Follow-Up Visits

#### 8.3.1. 24-Hour Follow-Up Visit

Subjects in all 3 cohorts should be scheduled for an on-site follow-up visit 24 hours ( $\pm$  3 hours) after the completion of the plasma infusion. During this visit, the following procedures will be performed:

- Review of medical history, concomitant medications, and AEs since the infusion visit;
- Conduct a complete physical examination that includes measurement of, body weight, and vital signs (blood pressure, heart rate, respiration rate, and temperature), and evaluation of cardiopulmonary systems, basic neurological function, and presence of DVT, cardiac ischemia, or PE. DVT will be assessed in conjunction with a subjects' D-Dimer test results and Wells scale score; and
- Collect urine and blood samples as noted for all tests listed in the Schedule of Events tables (Table 4, Table 5, Table 6, and Table 8).

**NOTE:** Since subjects in Cohort 3 receive 2 separate infusions, a 24-hour post-infusion follow-up visit will be scheduled after each infusion.

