## 8.3.2. Telephone Follow-Up

In addition to scheduled on-site follow-up visits, subjects in all 3 cohorts will be contacted by phone at 48 hours ( $\pm$  2 hours), 72 hours ( $\pm$  2 hours), and 14 days ( $\pm$  2 hours) (ie, Study Days 3, 4, and 15) after the completion of the plasma infusion. During the calls, subjects will be asked specific questions (Appendix H) regarding possible signs and symptoms of any AEs they may have experienced and any concomitant medications taken since the infusion visit. The date and time of the call, as well as the subject's responses will be recorded in the source documents and the eCRF.

Cohort 3 subjects' will have no 14- day follow-up phone call after the first infusion since it would occur on the same day as the second infusion (Study Day 15). The 14-day follow-up phone call subsequent to the second infusion visit will occur on Study Day 29.

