# 8.3.3. 7-Day Follow-Up Visit

A post-infusion follow-up visit will be scheduled 7 days ( $\pm$  1 day) post-infusion for subjects in all 3 cohorts. The following procedures will be performed at these visits:

- Review of medical history, concomitant medications, and AEs since the last telephone follow-up contact;
- Abbreviated physical exam which includes vital signs (blood pressure, heart rate, respiration rate, and temperature) and a general assessment of health; and
- Collect blood samples as noted for all tests listed in the Schedule of Events tables (Table 4, Table 5, Table 6, and Table 8).

**NOTE:** Since subjects in Cohort 3 receive 2 separate infusions, a 7-day post-infusion follow-up visit should also be scheduled after the second infusion. The second 7-day post-infusion follow-up visit will also follow the procedures described in this section.

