### 8.3.4. 28-Day Follow-Up Visit

A post-infusion follow-up visit will be scheduled 28 days ( $\pm$  1 day) post-infusion for subjects enrolled in Cohorts 1 and 2. For subjects enrolled in Cohort 3, a 28-day post-infusion follow-up visit will take place after the second plasma infusion, only, approximately 42 days after the first infusion visit. The following procedures will be performed at these follow-up visits:

- Review of medical history, concomitant medications, and AEs since the 14-day telephone follow-up contact;
- Abbreviated physical exam which includes vital signs (blood pressure, heart rate, respiration rate, and temperature) and a general assessment of health;
- Collect blood samples as noted for all tests listed in the Schedule of Events tables (Table 4, Table 5, Table 6, and Table 8); and
- Exit interview concluding the subject's study participation.

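### The telephone script's symptom checklist looks back only 24 hours, so at the 14-day call it misses about six of the seven days since the last contact

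*Protocol*

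**What the plan says.** Protocol Appendix H is headed for use at all three post-infusion calls. Its symptom table has a single lead-in, "last 24 hours have you", and none of the nine prompts beneath it (chest pain, shortness of breath, calf pain and blood in urine or stool among them) has a recall period of its own. Symptoms reported here go to the Adverse Event CRF.

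Other wording in the protocol looks back further:

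- The script's introduction asks about medical problems and medications and refers to "your last visit to the blood" center.
- Item 2 of the script asks "Are you currently taking any medications since the last visit".
- Section 8.3.2 sends the calls to Appendix H for "any AEs they may have experienced and any concomitant medications taken since the infusion visit".

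The on-site reviews run from contact to contact:

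- 24-hour visit (8.3.1): "Review of medical history, concomitant medications, and AEs since the infusion visit"
- 7-day visit (8.3.3): "AEs since the last telephone follow-up contact"
- 28-day visit (8.3.4): "Review of medical history, concomitant medications, and AEs since the 14-day telephone follow-up contact"

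In Cohort 3, a footnote to Table 8 says: "The 14-day follow-up phone call will only occur after Infusion Visit #2".

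**The concern.** The on-site visits form a chain in which each review starts where the previous contact ended. The symptom checklist breaks that chain at the 14-day call. A subject whose calf pain or breathlessness came and went on Day 10 can truthfully answer No on Day 15, and the 28-day review does not go back over that week.

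Section 6.1 rests the safety conclusion on TEAEs alone and counts them through the whole post-infusion follow-up. The schedule tables list only AEs and concomitant medications at the 14-day call, with no examination, vital signs or laboratory tests, so questioning is the only means of detection at that contact. In Cohort 3 the call after infusion 2 also closes the 14-day period within which section 11.1.1 generally attributes AEs to the most recent product.

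**Working it through.** **Inputs.** All are from the protocol.

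- Study days (section 6.8): in Cohorts 1 and 2, visits on Days 2, 8 and 29 and calls on Days 3, 4 and 15. In Cohort 3 after infusion 2, visits on Days 16, 22 and 43 and calls on Days 17, 18 and 29.
- Windows (sections 8.3.1 to 8.3.3): 24-hour visit ±3 h, calls ±2 h, 7-day visit ±1 day.
- Checklist recall (Appendix H): 24 h.

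**Study days reproduced.** With infusion on Day 1, the 7-day visit is 1 + 7 = Day 8 and the 14-day call is 1 + 14 = Day 15. With infusion 2 on Day 15, they are 15 + 7 = Day 22 and 15 + 14 = Day 29. Both agree with section 6.8.

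**Interval since the previous contact.** The nominal interval is the call time minus the previous contact time. The extremes come from moving each to the edge of its window.

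| Call | Previous contact | Nominal | Minimum | Maximum |
|---|---|---|---|---|
| 48-hour | 24-hour visit | 48 − 24 = 24 h | 46 − 27 = 19 h | 50 − 21 = 29 h |
| 72-hour | 48-hour call | 72 − 48 = 24 h | 70 − 50 = 20 h | 74 − 46 = 28 h |
| 14-day | 7-day visit | 336 − 168 = 168 h | 334 − 192 = 142 h | 338 − 144 = 194 h |

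**Time the checklist does not reach** (interval minus 24 h):

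- 48-hour call: nominally 0 h, at most 29 − 24 = 5 h.
- 72-hour call: nominally 0 h, at most 28 − 24 = 4 h.
- 14-day call: 168 − 24 = 144 h, ranging from 142 − 24 = 118 h to 194 − 24 = 170 h. That is 6.0 days (4.9 to 7.1).

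The unreached stretch runs from Day 8 to Day 14 in Cohorts 1 and 2, and from Day 22 to Day 28 in Cohort 3.

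**Number of calls.** Cohorts 1 and 2 have 16 subjects with 3 calls each, and Cohort 3 has 8 subjects with 5 each: 16 × 3 + 8 × 5 = 88. These counts per subject agree with SAP Table 2. Each subject has one 14-day call, so 24 of the 88 are affected.

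**The passages together.** The 7-day visit covers the time up to Day 8, and the 28-day visit covers the time from Day 15. The 14-day call is therefore the scheduled contact for the week between, and its checklist asks about the last day of it. Step C of the script names the next contact for the 48-hour and 72-hour calls only, which suggests that the form was not adapted when it was also assigned to the 14-day call.

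**The case against.** The strongest reply is that the week is already asked about. Section 10.5.1 requires AEs to be assessed at all study visits with an open-ended question, and its example reaches back to the last conversation. SAP section 2.2 counts the telephone contacts as visits. The schedule tables mark AEs at every call, the script's introduction mentions medical problems, and the 28-day visit repeats the health questionnaire. The Manual of Procedures and the separate telephone form are not among the documents and may say more. All of this stands. It is why the point is limited to a risk of under-recording, and section 10.5.1 does not itself set a look-back for a symptom checklist.

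The time phrase in section 8.3.2 could also attach to medications alone, and the script's introduction has the same ambiguity. That is a fair reading, but section 8.3.2 would still ask for any AEs experienced, which is wider than one day.

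A short window could be deliberate, as a screen for current symptoms alongside the open question. The documents do not say so, and the answers feed the Adverse Event CRF.

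Finally, section 5.6.1.4 describes AE monitoring up to 7 days after infusion, and section 7.6.3 defines completion at the 7-day visit. The affected days fall after both, but section 6.1 counts TEAEs through the whole follow-up.

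**Conclusion.** The concern holds. The checklist's recall period is narrower than section 8.3.2 calls for and does not suit the 14-day call, where it leaves 144 of 168 hours (118 to 170 with the windows) outside the structured prompts. The mismatch is negligible at the 48-hour and 72-hour calls.

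The practical effect is modest: one call per subject, and only symptoms that resolve before the last day and do not emerge under the general questions. The documents give no AE timing, so no number or share of missed events can be stated. The conclusion assumes that Appendix H is used as printed. Confidence is high on the wording and the intervals, and lower on what staff actually ask at the 14-day call. The change should be made because it is cheap and bears directly on the primary endpoint.

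**What to change.** Reword the Appendix H lead-in so that the nine prompts ask about the time since the subject's last study contact. With the reviews in sections 8.3.1, 8.3.3 and 8.3.4, that gives an unbroken sequence from infusion to the 28-day visit and leaves the first two calls essentially as they are. Giving section 8.3.2 the same look-back is optional but would remove its ambiguity.

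The cost is a change to one script, and to one sentence if section 8.3.2 is aligned, with the review and approval before use that section 14.1.2 requires. No visits, samples or staff are added. The trade-off is about 7 days of recall instead of 1 on a single call, so onset dates and times may be less exact there and counts of minor AEs may rise slightly.

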## 10.5.1. Methods and Timing for Assessing, Recording, and Analyzing Adverse Events

All AEs will be assessed at all study visits, documented in the source records, and recorded on the eCRFs using accepted medical terms and/or the diagnoses that accurately characterize the event. When a diagnosis is known, the AE term recorded on the eCRF will be the diagnosis rather than a constellation of symptoms. The PI will assess and record for all AEs/SAEs: a description of the event (if the event consists of a cluster of signs and symptoms, a diagnosis should be recorded rather than each sign and symptom); onset date and time, and stop date and time; intensity (recorded as mild, moderate or severe); seriousness; causality (relationship to study drug); outcome (eg, resolved, resolved with sequelae, not resolved, fatal, or unknown if applicable); action taken with the study agent (eg, no action, study agent discontinued and other action taken).

When an event is not resolved by study closure, it will be documented on the AE eCRF as ""not recovered/not resolved".

AEs will be assessed using an open-ended question such as: "How have you been feeling since we last spoke?" If an AE that requires medical attention is reported to a nurse, it should be reported to a study physician immediately. The PI or study physician will assess subjects for any medical side effects, through a focused review of systems and physical exam. Specifically, they will be looking for evidence of coagulation disturbances. Subjects with suspected positive findings will be referred to their treating physicians for clinically indicated and appropriate evaluation and management. Acute plasma infusion reactions will also be specifically documented as follows:

- Fever (by oral or axillary temperature);
- Allergic reactions (i.e., skin rash; urticarial; pruritus; generalized flushing; localized angioedema; edema of the lips, tongue, or uvula; erythema of the periorbital area; conjunctival edema by physical exam);
- Bronchospasm (by symptoms);
- Chills (by subject report after specific query by clinical staff);
- Tachycardia, bradycardia, other dysrhythmias, dyspnea, hypertension, hypotension (by vital sign measurements heart rate, blood pressure, and respiration rate);
- Hemolysis or acute hemolytic transfusion reactions resulting in circulatory/cardiovascular dysfunction (by clinical laboratory result); and
- Infection (by physical exam or clinical laboratory results).

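### The telephone script lacks the open-ended adverse-event question, and the chills query, that protocol section 10.5.1 calls for, and the next in-person visits look back only to the last call

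*Protocol*

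**What the plan says.** Protocol section 10.5.1 sets the rule for finding adverse events. On where it applies: "All AEs will be assessed at all study visits". On how: "AEs will be assessed using an open-ended question such as", followed by an example that asks how the subject has felt since the previous contact. The same section lists acute infusion reactions to be documented specifically, each with its method. One entry reads "Chills (by subject report after specific query by clinical staff". Fever is to be found by temperature measurement, and infection by examination or laboratory result.

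SAP section 2.2 counts the 48-hour, 72-hour and 14-day telephone contacts as follow-up visits. Protocol section 8.3.2 sends those calls to the questions in Appendix H.

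Appendix H has nine yes/no symptom rows: headache, vision or hearing, strength or sensitivity, chest pain, shortness of breath, abdominal pain, leg swelling or calf pain, "Rash or unusual bruising on your skin", and blood in urine or stool. The only other question about the subject's health is "2. Are you currently taking any medications since the last visit".

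The in-person reviews start where the calls stop. The 7-day visit (section 8.3.3) covers "AEs since the last telephone follow-up contact". The 28-day visit (section 8.3.4) covers "AEs since the 14-day telephone follow-up contact".

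**The concern.** Protocol section 6.1 rests the safety conclusion on TEAEs alone, and section 6.5 makes their absence part of the condition for moving to the next dose cohort. How TEAEs are elicited is therefore how the primary endpoint is measured.

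A caller who follows Appendix H as printed does not ask the open question, and the next in-person visit is not instructed to go back over the same interval. Events that the protocol itself anticipates fall outside the nine prompts. Section 5.6.1.4 names nausea, light-headedness, fainting, tingling and cramping among the expected risks, and fever and back pain among the rarer ones. The worksheet in Appendix I has boxes for chills, fever and nausea or vomiting. If such an event begins and ends between contacts, is not treated, and is not volunteered, nothing in the script would bring it out. The error runs in one direction, towards too few TEAEs.

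**Working it through.** The plan states no figure for this point. The check sets the passages side by side and then does interval arithmetic on the visit schedule.

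**Step 1: the rule against the script.**

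| Section 10.5.1 | Appendix H |
|---|---|
| Open-ended question at all study visits | None. Nine closed rows, a medication item, then the scheduling and form-completion steps |
| Chills by specific query (listed as an acute reaction) | No query |
| Fever by measured temperature | No prompt, but a call could not apply the stated method |
| Infection by examination or laboratory | No prompt, but a call could not apply the stated method |

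The first row is a contradiction. The second is a departure, softened because section 10.5.1 lists chills as an acute infusion reaction. The last two rows are gaps in coverage, not contradictions.

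The script's introduction mentions medical problems, but only to announce the questions that follow. Some words of Appendix H are clipped in the text available. Even so, the order of items (nine rows, item 2, then C and D) leaves no place for a lost open question.

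**Step 2: which intervals are left to the script.** The day of infusion is Day 1.

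- The 24-hour visit reviews events since infusion, in person.
- The 48-hour and 72-hour calls follow. The 7-day visit then starts its review at the 72-hour call, so 24 to 72 hours is left to the calls: 72 − 24 = 48 h.
- The 14-day call follows the 7-day visit. The 28-day visit then starts its review at that call, so Days 8 to 15 are left to it: 15 − 8 = 7 days = 168 h.

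**Step 3: share of follow-up.**

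- Cohorts 1 and 2, and Cohort 3 after the second infusion: 48 + 168 = 216 h = 9 days. Follow-up is 28 × 24 = 672 h. 216 / 672 = 32%.
- Cohort 3 after the first infusion: section 8.2.2 requires an in-person review before each infusion, worded to reach back to the collection visits, and section 8.3.2 says there is no 14-day call. Days 8 to 15 are therefore not left to the script. The 48 h between 24 and 72 hours are left to it at the 7-day visit, but the second-infusion visit formally takes them in again.
- Cohort 3 over both infusions (42 × 24 = 1,008 h): 48 + 48 + 168 = 264 h, or 264 / 1,008 = 26%. If the second-infusion review is credited for the first 48 h, it is 216 / 1,008 = 21%.

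**Step 4: what one missed subject does.** With 4 subjects per arm in Cohorts 1 and 2 and 8 per cohort, one subject whose only TEAE is missed lowers the incidence by 1/4 = 25 points in the arm or 1/8 = 12.5 points in the cohort. The DSMB is guaranteed data only through the 7-day visit (section 6.5), so the two early calls feed the decision to escalate.

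**The case against.** The strongest reply is that nothing says Appendix H replaces section 10.5.1. Section 8.3.2 says only that specific questions are asked, so staff remain bound to the open question on the calls as well. The script's introduction may invite a report, there is a comment column, and the medication question can reveal treated events. The 7-day and 28-day visits also include the standardized health questionnaire, an abbreviated examination, vital signs and a blood count, with chemistry at Day 7, so an event still present then would be met in person. Section 6.3 leaves further detail to a Manual of Procedures that is not among the documents.

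Much of this stands, and it rules out four stronger readings that a reader might infer:

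- *That events outside the nine prompts are never asked about.* The rule in section 10.5.1, the medication question and the later visits all offer a route. The exposure is limited to events that are transient, untreated and not volunteered.
- *That leaving out fever and infection breaks section 10.5.1.* That section finds them by measurement, examination or laboratory, and lists them as acute reactions.
- *That the script alone covers Days 8 to 15 for everyone.* It does not after the first infusion in Cohort 3.
- *That the loss can be put as a percentage of events.* One could multiply 9/27 = 33% of the time after 24 hours by a guessed share of events outside the prompts; 25 to 75% would give 8 to 25%. The documents support neither uniform onset nor any such share.

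The reply does not remove the mismatch. A script is written to be followed, and this one, followed as printed, omits the question the protocol requires. The narrow look-back means no later visit is instructed to recover what was not asked.

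**Conclusion.** The point holds in limited form. Appendix H does not carry out the open-ended elicitation that section 10.5.1 requires at all study visits, and it has no chills query. Together with the look-back wording of sections 8.3.3 and 8.3.4, this formally leaves 9 of 28 days (32%) to closed prompts after the single infusion in Cohorts 1 and 2 and after the second infusion in Cohort 3. Any resulting bias in TEAE incidence is downward, and its size cannot be estimated from the documents.

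The conclusion rests on two assumptions: that callers keep to the script as printed, and that the Manual of Procedures does not add the open question. The change should be made because it is nearly free and bears on the primary endpoint, but the point does not invalidate the design.

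**What to change.** 1. Open Appendix H with the example question printed in section 10.5.1 and give it a recorded free-text answer.
2. Add a query for chills, and preferably one for fever. Further symptom prompts are optional.
3. In sections 8.3.3 and 8.3.4, have the 7-day and 28-day visits review adverse events since the previous in-person visit instead of since the last call.

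The cost is a revised script, two lines of protocol wording, IRB approval of both, and a minute or two more per call. No dose, visit date or treatment rule changes.
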